3.3 Sub Studies

Swab Sub-Study

We will randomly select participants to collect additional swab samples in a sub-study. In addition to the regular treatment and questionnaire activities, the participants of the sub-study may be asked to:

1. Self-collect a nasal, rectal, and/or saliva swab at baseline, days 3, 7, and/or 14

Participants may participate in the main study swabs at Day 3 or the swab sub-study or they may opt not to collect swabs at all. Participants in the sub-study will not collect double swabs at day 3. Swabs will only be collected once.

[figure not shown]
The figure below outlines the possible paths for participants interested in collecting swabs.

Participants may:

- 1) Only collect swabs at Day 3 as part of the main study. These participants will collect up to 3 swabs total.
- 2) Collect swabs at Baseline, Day 3, Day 7, and/or Day 14 as part of the sub-study. These participants will collect up to 4 nasal swabs, 4 rectal swabs, and 4 saliva swabs (up to 12 swabs total).

Patients may also opt not to collect swabs. All patients will be randomized in the same fashion as one group, despite the patient's decision to collect swabs or not.

Figure 1:

We plan to place patients into one of three groups for the swab sub-study or a fourth group into the main study. The first 300 participants agreeing to take part in the sub-study will be in Group 1. The next 300 will be in Group 2. The last 300 will be in Group 3. All other willing participants will be placed in Group 4 as part of the main study. The groups are outlined below:

Group 1=

- Nasal Swab at Day 0
- Nasal & Saliva Swab at Day 3

Group 2=

- Nasal & Saliva Swab at Day 3
- Nasal Swab at Day 7

Group 3=

- Nasal, Saliva, Rectal Swab at Day 3
- Nasal, Saliva, Rectal Swab at Day 14

Participants who are willing to take part in the main study swabs but not in the sub-study swab group will be placed in Group 4 automatically.

Group 4=

- Nasal, Saliva, Rectal Swab at Day 3

Hospitalization Verification Sub-Study

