5.2 Enrollment

Interested participants will be remotely screened for eligibility prior to enrollment. Participants can be screened by phone or by an electronic REDCap form accessible from the study website. If eligible, study staff will call the participant and collect informed consent electronically via DocuSign. Upon determining eligibility and signing electronic informed consent documents, study staff will ask the participant to provide their mailing address. Study staff will then mail the participant their randomized treatment allocation, self swabbing materials, and email an electronic baseline questionnaire. No contact between study staff and participants in this trial will take place as to minimize risk of infection spread. At the end of the screening questionnaire, we will collect phone number and email information from the eligible participants. We will also require patients to provide proof of their positive test result by uploading documentation through REDCap.

The data analyst will inform the coordinator daily of the new eligible participants. Coordinators will then call participants to review the study and informed consent form.

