5.3 Baseline Assessment

Once a participant is determined eligible for the study and informed consent has been signed, they will be asked to complete an electronic baseline questionnaire via REDCap. Participants will be asked to provide information about their health and contact information in order to facilitate follow-up. Next of kin information will be collected in the event that the patient is unresponsive due to hospitalization or death. Please see the questionnaire in the appendix.

Participants unable or unwilling to electronically complete the questionnaires themselves may call the study coordinator who can fill out the survey on their behalf over the phone. Participants may also utilize a designated alternate, such as a family member, to fill out the electronic questionnaire on their behalf. The coordinator will make a note on the patient Masterfile if they filled out a questionnaire on the subject’s behalf.

A sub-set of participants in the swab sub-study will be asked to collect a nasal swab at baseline.

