8.6 Laboratory Technicians

- Prepare patient study kits with all materials needed for the study
- Organize study supplies
- Prepare patient information sheets and swab instructions
- Scan swabs received from the participants into the REDCap database
- Assist with laboratory analysis of samples
- Assist with biobanking and storage of specimens

9 Statistical Methods

Please see the Statistical Analysis Plan for details on pre-specified statistical methods for this trial.

The primary analysis will estimate the risk difference (RD) and risk ratio (RR) comparing azithromycin to placebo. We will estimate these parameters using a logistic regression model with a single covariate for treatment arm. We will estimate the RD and RR from the logistic regression using marginal standardization, and a bootstrap for 95% confidence intervals [5,6]. We will compute *P*-values for differences between arms using a permutation test with the difference between arms as the test statistic and 10,000 iterations.

The secondary analysis of viral load will compare log transformed values of relative read and number of reads using a t-test. We will compute *P*-values for differences between arms using a permutation test with the difference between arms as the test statistic and 10,000 iterations.

Determination of statistical significance for the primary and secondary analysis will follow the final alpha-spending function determined by the group sequential design.

10 Study Medication

The study drug product will be obtained from Pfizer, Inc. Participants enrolled in the study will be offered a dose of oral azithromycin or placebo determined by their randomization allocation. We will monitor adverse events following treatment as described in Chapter 9.

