### *Outcomes with a prevalent measure at Day 3:*

We will estimate the difference in prevalence between arms and the 95% confidence interval for the difference. We will compute *P*-values for differences between arms using a permutation test with the prevalence difference between arms as the test statistic and 10,000 iterations.

- **Prevalence of positive swabs:** we will compare the prevalence of SARS-CoV-2 positive swabs at Day 3 after treatment in self-collected nasal, saliva, and rectal swabs in azithromycin compared to placebo-treated participants.
- **Genetic macrolide resistance determinants:** We will evaluate the prevalence of genetic macrolide resistance determinants *ermB*, *mefA/E*, and *mphA* by targeted PCR in rectal samples collected at Day 3 after treatment.
- **Adverse events:** we will conduct an adverse event survey at Day 3 after treatment, including gastrointestinal side effects (nausea, vomiting, diarrhea, abdominal pain) and rash. We note that some COVID-19 patients report gastrointestinal symptoms, and this survey will provide data on whether azithromycin causes additional gastrointestinal effects beyond those symptoms. We also note that adverse events will be cumulative through Day 3 and measure cumulative incidence (risk) not prevalence.

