### *Outcomes with a continuous measure at Day 3:*

We will compare log transformed values of relative read and number of reads using a t-test. We will compute *P*-values for differences between arms using a permutation test with the difference between arms as the test statistic and 10,000 iterations.

- **Viral load:** we will assess viral load by RT-PCR in self-collected nasal, saliva, and rectal swabs at Day 3 after treatment.

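### The Day 0 nasal swab collected from Group 1 has no planned use; adjusting Day 3 nasal viral load and positivity for it would be a near-free gain in precision

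*SAP*

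**What the plan says.** Under SAP 6.2, continuous measures at Day 3, viral load is the outcome: "we will assess viral load by RT-PCR in self-collected nasal, saliva, and rectal swabs at Day 3 after treatment". The method is "We will compare log transformed values of relative read and number of reads using a t-test", with P-values obtained "using a permutation test with the difference between arms as the test statistic and 10,000 iterations". Protocol 9 repeats it: "The secondary analysis of viral load will compare log transformed values of relative read and number of reads using a t-test". For positivity, SAP 6.2 states "we will compare the prevalence of SARS-CoV-2 positive swabs at Day 3 after treatment", with an unadjusted prevalence difference and permutation P-value.

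Protocol 3.3 places the first 300 sub-study volunteers in Group 1, whose schedule begins with "Nasal Swab at Day 0" and continues with nasal and saliva swabs at Day 3. Protocol 5.3 confirms it: "A sub-set of participants in the swab sub-study will be asked to collect a nasal swab at baseline". Groups 2, 3 and 4 give Day 3 nasal swabs but none at Day 0. Neither document names an analysis of the Day 0 swab, and it is not among the baseline covariates listed in SAP 6.3.

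On timing, Protocol 5.2 says: "Study staff will then mail the participant their randomized treatment allocation, self swabbing materials, and email an electronic baseline questionnaire". Protocol 3.8 places baseline activities on Day 0 and treatment on Day 1. Protocol 10.7 asks at Day 3 whether, and on which date, the drug was taken.

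**The concern.** Protocol 4.1 admits people up to seven days after they receive a test result, so viral load at entry can be expected to vary between participants. Randomization is neither stratified nor blocked (SAP 3.2), so nothing but chance balances it. In an unadjusted Day 3 comparison, whatever part of the Day 3 spread the starting value could explain stays in the error term. For Group 1 the starting nasal value will be in hand.

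Viral load and swab positivity are the trial's virologic outcomes, and the background in Protocol 2.1 is antiviral, so precision here has some value.

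The swab serves as a covariate only if it was taken before the dose. Drug and swab materials travel in the same kit after consent, so the swab cannot be taken on the calendar day of consent. The nasal instructions in Protocol 6.1 mention Days 3, 7 and 14 but no baseline swab. No supplied text states the order of swab and dose.

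**Working it through.** **No figure to reproduce.** The documents give no sample size, SD, target difference or power for viral load.

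**Inputs**
- N = 455, 2:1 allocation (SAP 3.2 and 3.3).
- Group 1: up to 300 (Protocol 3.3). Swabs are optional (Protocol 5.5).
- r, the correlation of Day 0 with Day 3 log nasal viral load: assumed, 0.2 to 0.7.
- f, the share of Day 3 nasal swabs that have a Day 0 swab: unknown. If all 455 swab and Group 1 fills, f = 300/455 = 0.66. One third is a less favourable case. If everyone who swabs is in Group 1, f = 1.

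**Where a baseline exists (f = 1).** Adjustment multiplies the variance by 1 − r²: 0.96, 0.91, 0.75 and 0.51 for r = 0.2, 0.3, 0.5 and 0.7. With 300 evaluable at 2:1 and 80% power, the detectable difference is (1.96 + 0.842) × √(1/100 + 1/200) = 0.343 SD unadjusted. Multiplying by √(1 − r²) gives 0.336, 0.327, 0.297 and 0.245 SD.

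**Whole Day 3 nasal comparison.** Combine the adjusted estimate from those with a baseline and the unadjusted estimate from the rest, weighting each by its precision:

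variance ratio = 1 / [f/(1 − r²) + (1 − f)]

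Example, f = 0.66 and r = 0.5: 1 / [0.659/0.75 + 0.341] = 1/1.220 = 0.82. The power column is for a test with 80% power unadjusted.

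| f | r | Variance ratio | Fall in variance | Power |
|---|---|---|---|---|
| 0.66 | 0.2 | 0.97 | 3% | 81% |
| 0.66 | 0.3 | 0.94 | 6% | 82% |
| 0.66 | 0.5 | 0.82 | 18% | 87% |
| 0.66 | 0.7 | 0.61 | 39% | 95% |
| 1/3 | 0.2 | 0.99 | 1% | 81% |
| 1/3 | 0.3 | 0.97 | 3% | 81% |
| 1/3 | 0.5 | 0.90 | 10% | 84% |
| 1/3 | 0.7 | 0.76 | 24% | 90% |

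Simulation with 364 evaluable participants and f = 0.66 gave 0.95, 0.83 and 0.60 at r = 0.3, 0.5 and 0.7, and 1.01 at r = 0. The unadjusted estimate showed no bias.

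**What an unweighted model delivers.** The table assumes that participants with a baseline, whose residual variance is smaller, get more weight. Ordinary least squares with a missing-baseline indicator weights everyone equally. The average residual variance is then f(1 − r²) + (1 − f), so the ratio is 1 − f·r². At f = 0.66 this is 0.97, 0.94, 0.84 and 0.68; at f = 1/3 it is 0.99, 0.97, 0.92 and 0.84. The difference matters only when r is high. A short simulation agreed: at f = 0.66 and r = 0.7 it gave 0.68 unweighted and 0.62 weighted by baseline status.

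**Restricting to Group 1 can cost precision.** An adjusted analysis of Group 1 alone, against the planned test in everyone, has variance ratio (1 − r²)/f. At f = 0.66 that is 1.38, 1.14 and 0.77 for r = 0.3, 0.5 and 0.7. Participants without a baseline must stay in.

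**Other specimens.** Group 1 gives no rectal swab, and its saliva is collected at Day 3 only. Neither comparison can gain.

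**The case against.** The planned t-test and permutation test are valid under randomization without any baseline, viral load is one of about ten secondary outcomes, and no power claim rests on it. That stands: a reader who inferred an invalid or biased analysis would go beyond the documents.

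The gain rests on an undocumented correlation. That also stands. At r = 0.2 to 0.3 and f = 0.66, the standard error falls by only about 1% to 3%. It is also tempting to apply the full 1 − r² factor to the whole comparison, but Groups 2 to 4 contribute Day 3 nasal swabs without a baseline and dilute it.

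On timing, a reader might infer that the Day 0 swabs are post-dose. The documents do not show that. The swab is labelled Day 0 and baseline, the schedule puts treatment on Day 1, and the instructions listed among the kit contents in Protocol 5.10 are not supplied and may settle the order. What remains is that the supplied text does not.

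Finally, Group 1 is filled first, and Day 14 data already existed by December 2020 (Protocol 3.5). A new instruction cannot reach swabs already taken, and a strict rule requiring a clock time could discard usable ones. The fix has to allow for this.

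**Conclusion.** The point holds as a missed efficiency gain, not an error. A nasal baseline is planned for up to 300 participants, and no stated analysis uses it. The gain is confined to Day 3 nasal viral load and nasal positivity; the percentages above were worked for log viral load.

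It ranges from negligible (variance down 1% to 6% at r of 0.2 to 0.3) to material (10% to 39% at r of 0.5 to 0.7), over f of one third to 0.66. Those figures assume precision weighting; an unweighted model gains somewhat less at high r. They also assume that a Day 0 swab used as covariate was taken before the dose.

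Viral load should not be read as the only virologic test of the antiviral rationale, since swab positivity is a separate outcome.

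**What to change.** **SAP 6.2, before laboratory processing** (Protocol 7 leaves all processing to the end of the trial):
- Model nasal Day 3 log viral load on arm, Day 0 log nasal viral load and a missing-baseline indicator. Include everyone with a Day 3 nasal swab, not Group 1 alone. Allow the residual variance to differ by baseline availability if the gain in the table is wanted.
- Use the adjusted arm coefficient as the permutation statistic.
- Treat nasal Day 3 positivity in the same way, with Day 0 positivity as the covariate.
- Give undetectable values a stated fixed value and add an indicator for Day 0 detected or undetected.

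**Protocol 5.3:** state that the baseline swab is collected before study drug, with date and time recorded from then on.

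**Swabs already collected:** use as covariate those whose recorded collection date is not after the reported dosing date, with a sensitivity analysis that leaves out same-day swabs of unknown order. The documents do not say whether a collection date is recorded, so confirm this first.

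**Cost:** a few sentences, one instruction and slightly more analysis work; no extra swabs or visits. If r proves low, little is gained.

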### *Count outcomes:*

- **Number of emergency room visits:** during each online questionnaire we will survey patients about any emergency room visits (with stays <24 hours) that occurred since their last survey. We will model the total number of emergency room visits for each participant through 14 days as a count outcome using a negative binomial regression model with a single indicator for treatment arm and an offset for the number of days of follow-up completed by each participant. The exponentiated coefficient on the indicator will estimate the incidence rate ratio. We will compute a *P*-value for difference between arms using a permutation test with the coefficient from the model as the test statistic and 10,000 iterations.

## **6.3. Missing data**

If outcome data are missing for >15% of participants we will report results from sensitivity analyses for missing data [4,5]. We selected 15% missing because trials with >20% missing values are thought to be a concern for bias [6]. The primary analysis will account for censoring but will assume outcomes are missing completely at random. We will relax this assumption slightly, assuming that outcomes are missing at random (MAR) with an inverse-probability weighted (IPW) estimator using cumulative incidence through 14 days as the binary endpoint. We will model the probability of censoring as a function of baseline patient characteristics with a logistic regression model, and will use the inverse of the predicted probabilities from the model to re-weight the analysis population to reflect the full study population at the time of enrollment, using a doubly-robust targeted maximum likelihood estimator that also includes an outcome model using the same covariates [7]. Baseline characteristics used in the censoring model will include age, sex, race/ethnicity, zip code, comorbidities, concomitant medications, symptoms at enrollment, insurance status, alcohol use, tobacco/e-cigarette/marijuana use, and household composition. We will additionally consider a range of scenarios assuming the outcomes are missing not at random (MNAR), *i.e.* systematically, using a pattern mixture model approach described by Little et al. [4], whereby we model cumulative incidence through 14 days with a linear probability model as a function of covariates listed for the IPW estimator; missing outcomes will then be imputed using the model fit to predict, adding a shift parameter  $\Delta$  that we vary across a range of values.

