5.6 Day 7 Assessment

Participants will complete a questionnaire 7 days post baseline. The questionnaire will ask about the patient's health status and hospitalization status. The REDCap questionnaire will be sent electronically to the patient's email address.

A small subgroup of patients (100 per arm) will be asked to collect a rectal, saliva, and nasal swab at the Day 7 timepoint.

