5.8 Day 21 Assessment

A final electronic REDCap survey will be sent to participants at day 21. This is the final study questionnaire. The questionnaire will be similar to the Day 14 survey. Information about the patient's health and hospitalization status will be collected.

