### 3.3. Sample size

The trial's revised target enrollment is 455 participants, which will be sufficient to detect an increase in the proportion of patients who are symptom free 50% to 65% (15 percentage point increase) at 14 days from enrollment.

With 455 participants, the trial will have 80% power to detect an increase of 15 percentage points in the percentage of patients who are symptom free at 14-d under the following assumptions:

- 2:1 allocation ratio of azithromycin : placebo
- 50% symptom-free under placebo at the 14-day measurement (binomial outcome)
- 20% loss to follow-up
- 2-sided alpha of 0.05, power = 0.8.

- A single interim analysis with 50% of primary outcomes collected with stopping guideline determined using the Lan-DeMets spending function approach with an O'Brien and Fleming boundary.

The table below shows sample sizes under several effect size scenarios, assuming azithromycin increases the proportion of patients who are symptom free by 0.1 to 0.2 compared to placebo.

Sample size required for a fixed design allowing for 20% loss to follow-up. Calculations assume 2-sided alpha of 0.05 and 80% power.

p placebo	p azithro	RD	N placebo	N azithro	N Total
0.5	0.60	0.10	348	695	1,043
0.5	0.61	0.11	287	573	860
0.5	0.62	0.12	240	479	719
0.5	0.63	0.13	204	407	611
0.5	0.64	0.14	175	349	524
0.5	0.65	0.15	152	303	455
0.5	0.66	0.16	133	265	398
0.5	0.67	0.17	117	233	350
0.5	0.68	0.18	104	207	311
0.5	0.69	0.19	93	185	278
0.5	0.70	0.20	83	165	248

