## 6. Analysis

### 6.1. Outcome definitions

#### Primary Outcome:

The primary outcome will be free of symptoms at 14 days after the electronic enrollment assessment. Symptoms include: cough, fever, myalgia, anosmia, shortness of breath (and related abilities such as ability to walk across a room or up a flight of stairs), fatigue, conjunctivitis, and orthostatic symptoms.

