#### Secondary Outcomes:

- **Hospitalization and/or death by 14 days** after the electronic enrollment assessment.
- **Hospitalization/death by 21 days:** we will extend follow-up beyond the primary endpoint to capture any hospitalizations or death that progress more slowly and are not detected by 14 days.
- **Adverse events:** we will conduct an adverse event survey at Day 3 after treatment, including gastrointestinal side effects (nausea, vomiting, diarrhea, abdominal pain) and rash. We note that some COVID-19 patients report gastrointestinal symptoms, and this survey will provide data on whether azithromycin causes additional gastrointestinal effects beyond those symptoms.
- **Prevalence of positive swabs:** we will compare the prevalence of SARS-CoV-2 positive swabs at Day 3 after treatment in self-collected nasal, saliva, and rectal swabs in azithromycin compared to placebo-treated participants.
- **Viral load:** we will assess viral load by RT-PCR in self-collected nasal, saliva, and rectal swabs at Day 3 after treatment.
- **Mortality:** we will collect emergency contact/next of kin information during the baseline questionnaire. We will follow-up with the emergency contact if participants are lost to follow-up at the Day 14 and Day 21 questionnaires to assess mortality and hospitalization outcomes.
- **Genetic macrolide resistance determinants:** We will evaluate the prevalence of genetic macrolide resistance determinants *ermB*, *mefA/E*, and *mphA* by targeted PCR in rectal samples collected at Day 3 after treatment.
- **COVID-19 symptoms at 21 days:** we will ask patients about COVID-19 symptomology during each online questionnaire, including cough, fever, myalgia, anosmia, shortness of breath (and related abilities such as ability to walk across a room or up a flight of stairs), fatigue, conjunctivitis, and orthostatic symptoms.
- **Number of emergency room visits:** during each online questionnaire we will survey patients about any emergency room visits (with stays <24 hours) that occurred since their last survey.
- **Number of household members with COVID-19 (confirmed or symptomatic):** during each online questionnaire we will ask participants how many of their household members have symptoms of COVID-19 or confirmed disease.

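### SAP 6.3 builds its missing-data sensitivity analyses on baseline covariates only and leaves out the scheduled Day 7 and Day 21 symptom reports, so it cannot fully correct dropout that depends on recovery after enrollment

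*SAP*

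**What the plan says.** SAP 6.1 defines the endpoint: "The primary outcome will be free of symptoms at 14 days after the electronic enrollment assessment". Under SAP 6.3 the primary analysis assumes that outcomes are missing completely at random. If more than 15% are missing, two sensitivity analyses follow.

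- **Missing at random.** An inverse-probability-weighted, doubly robust TMLE: "We will model the probability of censoring as a function of baseline patient characteristics with a logistic regression model". The outcome model uses the same covariates. The list is entirely baseline, and its only symptom item is symptoms at enrollment.
- **Missing not at random.** A pattern-mixture imputation from the same covariates, plus a shift Δ whose range is not stated.

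Later symptom data are scheduled. The timeline in Protocol 3.8 lists a hospitalization and symptoms questionnaire at Days 7, 14 and 21, and SAP 6.1 says "we will ask patients about COVID-19 symptomology during each online questionnaire". The descriptions in Protocol 5.6 ("The questionnaire will ask about the patient's health status and hospitalization status") and 5.8 ("Information about the patient's health and hospitalization status will be collected") speak of health in general, so the timeline and SAP 6.1 are the firmer support. Protocol 5.8 does not limit the Day 21 survey to people who answered at Day 14.

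If Day 14 is missed, Protocol 5.7 has staff ask the next of kin for vital status and hospitalization. Symptom status is not recovered that way.

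**The concern.** Day 7 symptom status is an earlier reading of the primary endpoint. In a remote trial, whether someone answers at Day 14 may well depend on how they felt a week before. If so, outcomes are not missing at random given baseline alone, and a baseline-only model leaves out the same driver that the complete-case analysis leaves out. The two could agree for that reason, and the agreement could be read as support.

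The analysis is likely to be run, because SAP 3.3 plans for 20% loss, above the 15% trigger. The likely origin is the change of endpoint. The SAP version 5 text in the Appendix, written when hospitalization or death was primary, has nearly the same models, and the current section still speaks of cumulative incidence through 14 days. Next of kin can supply hospitalization or death. They are not asked about symptoms.

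**Working it through.** **1. The plan's own figure.** Inputs from SAP 3.3: 50% versus 65% symptom free, "2:1 allocation ratio of azithromycin : placebo", "2-sided alpha of 0.05, power = 0.8", 20% loss. With pooled proportion (0.50 + 2×0.65)/3 = 0.60:

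n(placebo) = [1.96·√(0.60×0.40×1.5) + 0.842·√(0.25 + 0.2275/2)]² / 0.15² = 125.97.

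Multiplying by 1.20 gives 151.2 and 302.3, rounded up to 152 + 303 = 455, the stated total. (Dividing by 0.80 would give 473; that is a separate matter.) At 20% loss, 0.20 × 455 = 91 outcomes are missing.

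**2. Assumptions not in the documents.** Symptom free at Day 7: 25% placebo, 40% azithromycin. Of these, 90% are still free at Day 14. Missingness depends only on arm and Day 7 status. Baseline covariates are uninformative about Day 7 status, so baseline weights are constant and the weighted result equals the complete-case result.

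**3. Day 14 rate among those not free at Day 7**, solved from the totals:
- placebo: (0.50 − 0.25×0.9)/0.75 = 0.367
- azithromycin: (0.65 − 0.40×0.9)/0.60 = 0.483

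**4. Observed proportion in an arm.** Let q be the Day 7 rate, b the rate from step 3, and r₁ and r₀ the missing fractions among those free and not free at Day 7:

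[q(1−r₁)0.9 + (1−q)(1−r₀)b] / [q(1−r₁) + (1−q)(1−r₀)]

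| Assumed pattern | Placebo r₁/r₀ | Azithromycin r₁/r₀ | Placebo | Azithromycin | Difference |
|---|---|---|---|---|---|
| Same in both arms | 30%/15% | 30%/15% | 0.482 | 0.631 | 0.149 |
| Opposite by arm | 10%/23.3% | 30%/13.3% | 0.517 | 0.629 | 0.113 |
| Reverse | 30%/16.7% | 10%/26.7% | 0.483 | 0.671 | 0.188 |

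The last two rows have 20% missing in each arm. The first has 0.25×0.30 + 0.75×0.15 = 18.75% in placebo and 0.40×0.30 + 0.60×0.15 = 21% in azithromycin. The error in the difference is about −0.1, −3.75 and +3.75 points. In the first row each arm's proportion is about 2 points low.

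**5. Range under other assumptions, at no true effect** (25% free at Day 7 and 50% at Day 14 in both arms).
- Same pattern in both arms (35%/15%): bias 0, with each arm reading 0.475 instead of 0.500.
- Azithromycin 35%/15%, placebo 20% at random: about −2.5 points.
- Azithromycin 35%/15%, placebo 5%/25%: −5.0 points. In 20,000 simulated trials of 303:152, a two-sided z test on observed outcomes rejected about 14% of the time.
- That last case, with a baseline covariate that moves the Day 7 rate by ±10 to ±25 points: the bias after baseline weighting shrinks to between −4.7 and −3.4 points.

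**6. With Day 7 status, by arm.** Placebo 0.25×0.9 + 0.75×0.367 = 0.50; azithromycin 0.40×0.9 + 0.60×0.483 = 0.65; difference 0.15. This follows from step 2, where Day 7 status alone drives dropout and is known for everyone.

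**7. The shift analysis.** In the opposite pattern, the true rates among the missing are (0.50 − 0.8×0.5167)/0.2 = 0.433 in placebo and (0.65 − 0.8×0.6292)/0.2 = 0.733 in azithromycin. The shifts needed from the observed rates are about −0.08 and +0.10. If predictions are arm-specific, one common Δ adds 0.2Δ to each arm and cancels from the difference. The SAP does not say whether Δ differs by arm.

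**The case against.** The case against is substantial.

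- **The difference is robust to a shared pattern.** The trial is masked with a matching placebo, and neither loss of interest after recovery nor silence when ill is specific to an arm. The error is then 0.1 point, and exactly zero under the null. The larger figures need dropout to depend on recovery in opposite directions in the two arms, and nothing in the documents makes that likely. This stands, and it limits the size.
- **Baseline covariates do some work.** The list includes symptoms at enrollment, age, comorbidities and concomitant medications. A reader might infer that the planned analysis cannot correct recovery-driven dropout at all. Step 5 shows a partial correction, so the supportable statement is that it cannot fully correct it.
- **Availability is unknown.** A reader might also infer that people who miss Day 14 often answer at Day 7 or Day 21. The documents give no such rate. Under Protocol 5.9, Day 14 non-responders have already had an email, a text and a call, so many may miss Day 21 too. A Day 7 report helps only those who gave one, and step 6 is true by construction.
- **The shift analysis exists.** It is meant for missingness that the covariates do not explain, and a wide enough range of arm-specific shifts would cover the errors shown. But its range is unstated, and it starts from predictions that ignore known Day 7 and Day 21 symptoms. It reduces the problem without removing it.

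**Conclusion.** The point holds in limited form. Both sensitivity analyses in SAP 6.3 use baseline covariates only, while symptom reports scheduled at Days 7 and 21 go unused. If dropout depends on recovery after enrollment, the missing-at-random analysis cannot fully correct it.

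The effect on the risk difference is close to nil if the pattern is the same in both arms. It is about 4 points either way under the assumed opposite patterns (11.3 or 18.8 instead of 15.0), with baseline covariates uninformative about Day 7 status. Stronger assumed contrasts reach about 5 points. All Day 7 rates and dropout patterns here are assumptions.

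The documents do not support reading this as a demonstrated bias in the trial's result. The primary estimate is not changed by the proposal. What improves is the check on it, which is likely to be needed at the planned 20% loss.

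**What to change.** In SAP 6.3, specify the missing-at-random analysis in one of two ways:

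1. Multiple imputation of the Day 14 symptom-free indicator, separately by arm, from the baseline covariates, Day 7 symptom status and, where present, Day 21 symptom status; or
2. Arm-specific weights for Day 14 response, or a longitudinal (sequential) TMLE, that include Day 7 status with a separate level for a missing Day 7 report.

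Two cautions belong in the text. Day 7 status arises after randomization, so it must not be entered as an ordinary adjustment covariate in the single-time-point treatment-effect model, where it could absorb part of the effect. Day 21 follows the outcome, so it belongs only in the imputation.

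Centre the missing-not-at-random shifts on these predictions, state their range, and say whether they may differ by arm. Report by arm how many participants without a Day 14 outcome have a Day 7 or Day 21 report, since that decides how much the change can help.

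The cost is a paragraph of SAP text and a little more programming. No new data are needed.
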